## 5.5. Randomization Stratification Factors

Randomization for this study is first stratified by AHP type: AIP [with genetic evidence of a mutation in the *HMBS* gene] vs non-AIP [HCP, VP, ADP, or any AHP without an identified mutation in a porphyria-related gene].

The AIP patient stratum is further stratified by the use of hemin prophylaxis or not immediately prior to Screening, and on the historical AAR. Patients who had been on hemin prophylaxis will be stratified by their historical AAR of  $<7$  vs  $\geq 7$ . Patients who had not been on a hemin prophylaxis will be stratified by their historical AAR:  $<12$  vs  $\geq 12$ . This historical AAR is calculated based on the medical record reviewed for inclusion criterion of at least 2 attacks requiring hospitalization, urgent healthcare visit or IV hemin administration at home within the 6 months prior to randomization.

Since only a few patients in the non-AIP stratum of HCP, VP, ADP, or any AHP without identified mutation in a porphyria-related gene are anticipated to be enrolled in the study, there is no further stratification within the stratum.

The historical AAR prior to randomization will be classified into high versus low when used as a categorical covariate. For patients on a hemin prophylaxis regimen at the time of screening, high attack rate is defined as  $AAR \geq 7$ . For patients not on a hemin prophylaxis regimen at screening,  $AAR \geq 12$  is considered as high attack rates.

Stratification factors are recorded in both the IRS and the clinical database. In statistical analyses that use randomization stratification factors as covariates, the stratum assignment will reflect the values as recorded in the clinical database. In the presence of stratification errors, the stratification used in analysis may not match that in the IRS. In addition, for non-AIP patients, the two AIP-specific stratification factors hemin prophylaxis regimen and historical AAR are collected in the clinical database and will be used as covariates in the analysis of AHP population.

## 5.6. Visit Windows

For PD and clinical laboratory parameters, analysis visits will be derived for the 6m-DB period based on the study day and visit windows. Target days and the acceptable range of study days for each visit are defined in [Table 1](#) below. If more than one visit falls within a visit window, the visit occurring closest to the target day will be selected. If there are multiple visits with the same distance from the scheduled visit day, the later visit will be selected. The derived visits will be used for all analyses.

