>5× to 8× ULN or Baseline	
 • Discontinue dosing when ALT >5× to 8× ULN and patient is symptomatic^b, or has TBL ≥2×ULN or INR >1.5 (for patients not on warfarin) and there is no alternative cause • For patients who are asymptomatic and do not have INR >1.5 or TBL ≥2x ULN: 
 – Hold dosing if ALT >5×ULN, until ALT recovers to ≤2×ULN – Dosing can be resumed when ALT recovers to ≤2 x ULN according to Section 6.2.3.1.1, and following discussion with the medical monitor • Perform weekly (±3 days) monitoring of LFTs per Table 7 and INR until ALT declines to 	
 • Discontinue dosing when ALT >5× to 8× baseline or >300 U/L (whichever is lower) and patient is symptomatic^b, or has TBL ≥2×ULN or INR >1.5 (for patients not on warfarin) and there is no alternative cause • For patients who are asymptomatic and do not have INR >1.5 or TBL ≥2x ULN: 
 – Hold dosing if ALT >5×baseline or >300 U/L (whichever is lower), until ALT recovers to ≤2×baseline – Dosing can be resumed when ALT recovers to ≤2 x baseline according to Section 6.2.3.1.1, and following discussion with the medical monitor

ALT Transaminase Level	Patients with Normal Baseline ALT	Patients with Elevated Baseline ALT ^a
	
$\leq 3 \times \text{ULN}$; then monitor every 2 weeks (± 7 days) until ALT level reaches $2 \times \text{ULN}$^c
 
 If the ALT elevation persists for ≥ 2 months, discussion with the medical monitor is required before continuing dosing. 	
 Perform weekly (± 3 days) monitoring of LFTs per Table 7 and INR until ALT declines to $\leq 3 \times \text{baseline}$; then monitor every 2 weeks (± 7 days) until ALT level reaches $2 \times \text{baseline}$^d If the ALT elevation persists for ≥ 2 months, discussion with the medical monitor is required before continuing dosing.
$> 8 \times \text{ULN}$ or Baseline	Discontinue dosing after confirmation if ALT $> 8 \times \text{ULN}$	Discontinue dosing after confirmation if ALT $> 8 \times \text{baseline}$ or $> 500 \text{ U/L}$ (whichever is lower)

Abbreviations: ALT=alanine aminotransferase; INR=international normalized ratio; LFT=liver function test(s); TBL=total bilirubin; U/L=units per liter; ULN=upper limit of normal

Note: In addition to these criteria, other assessments or evaluations may be performed per Investigator discretion, as appropriate.

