8.2.8. Safety Analyses

The primary safety parameter is the incidence of adverse events (AEs). Safety parameters also include vital signs, ECGs, clinical laboratory assessments, and physical exams. The extent of exposure will be summarized. The primary summaries of the safety of givosiran versus placebo will be based on safety parameters within the 6-month double-blind treatment period, using the Safety Analysis Set. Additional safety analyses will also be performed for the OLE period.

Adverse events will be classified according to the MedDRA System Organ Class and Preferred Term. AEs will be collected starting at the time the first dose of study drug is administered (Study

Day 1) through the duration of the study; SAEs will be collected starting at the time that informed consent is signed and through the duration of the study.

The number and percentage of patients experiencing AEs after the first dose of the study drug will be summarized for the following AE categories; additional categories may be specified in the SAP.

- Any AE
- Any AE that is assessed as related to study drug by the Investigator
- Any serious adverse event (SAE)
- Any AE leading to discontinuation of study drug
- Any AE leading to death

By-subject listings will be provided for deaths, SAEs, and AEs leading to study discontinuation. Incidence of adverse events of clinical interest will also be summarized by treatment group, and by-subject listings will be provided.

Descriptive statistics will be provided for clinical laboratory data and vital signs data, presented as both actual values and changes from baseline over time. Laboratory shift tables from baseline to worst values will be presented. Baseline will be defined as the last predose observation on or before Day 1. Abnormal physical examination findings and 12-lead ECG data will be presented in a by-patient data listing.

Descriptive statistics will be provided for ECG interval data and presented as both actual values and changes from baseline relative to each on-study evaluation and to the last evaluation on study. Details of any abnormalities will be included in patient listings.

Antidrug antibody results, including incidence and titer will be tabulated. A by-patient data listing will also be provided.

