**Table 1: Derived Analysis Visit Windows**

Study Visit	Target Day	Window
Screening	Day -60 to -1	$\leq -1$
Day 1	1	1
Week 2	15	2 – 22
Month 1	29	23 – 43
Month 2	57	44 – 71

Study Visit	Target Day	Window
Month 3	85	72 – 106
Month 4	113	107 – 127
Month 5	141	128 – 155
Month 6	169	156 - the earlier of (Day 183, and the day of the first dose of OLE)

For PD and laboratory parameters assessed during the OLE period and for vital signs and ECG measurements during the entire study, no windowing rules will be implemented, and the reported clinical visits will be used for analysis.

For QOL assessments including SF-12, EQ-5D-5L and missed days of work/school, data are collected every 3 months up to 12 months, then every 6 months afterwards. If the scheduled visits are not performed, any unscheduled and/or discontinuation visits will be mapped to the corresponding scheduled visits if the visit dates fall into below windows. The midpoint of two visits will be included in the time window of the preceding visit.

Scheduled visits (Month 3, 6, 9, 12)  $\pm$  6 weeks

Scheduled visits (Month 18, 24, 30, 36)  $\pm$  12 weeks

For patients who switched from placebo to givosiran, study visits will be mapped based on the redefined baseline.

The derived visits will be used for analyses.

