### **6.8.2. Laboratory Data**

Knowledge of several clinical laboratory tests, including ALA, PBG, and ALAS1, has the potential to unblind the reviewer. Procedures to protect the blind, including permissions to view these lab values, are described in the Data Integrity Plan (Amendment 3, 07Sep2018).

Clinical laboratory values will be expressed in Standard International (SI) units. Missing laboratory data will not be imputed.

Summary data for each laboratory parameter will be presented for each continuous clinical laboratory parameter (including hematology, serum chemistry, liver function tests and coagulation studies). Descriptive statistics will be presented for the actual values, change from baseline, and percent change from baseline by visit.

Shift tables will be employed to summarize the baseline category versus the “worst” post-baseline category for selected parameters.

A listing will be produced for amylase and lipase in all patient with amylase/lipase observations above  $3\times\text{ULN}$  flagged. A listing for all patients with abnormal liver function tests defined as an  $\text{ALT} >3\times\text{ULN}$ ,  $\text{AST} >3\times\text{ULN}$ , or total bilirubin  $>2\times\text{ULN}$  at any time point will also be provided.

A table will be produced to summarize the number and percentage of patients in each of below category at any post-baseline time point.

- $\text{ALT} >1 \ \& \ \leq 3$ ,  $>3 \ \& \ \leq 5$ ,  $>5 \ \& \ \leq 10$ ,  $>10 \ \& \ \leq 20$ ,  $>20\times\text{ULN}$ ,
- $\text{AST} >1 \ \& \ \leq 3$ ,  $>3 \ \& \ \leq 5$ ,  $>5 \ \& \ \leq 10$ ,  $>10 \ \& \ \leq 20$ ,  $>20\times\text{ULN}$ ,
- $\text{ALT or AST} >1 \ \& \ \leq 3$ ,  $>3 \ \& \ \leq 5$ ,  $>5 \ \& \ \leq 10$ ,  $>10 \ \& \ \leq 20$ ,  $>20\times\text{ULN}$ ,
- $\text{ALP} > 1.5\times\text{ULN}$ ,
- Total Bilirubin  $>1.5 \ \& \ \leq 2$ ,  $>2 \ \& \ \leq 3$ ,  $>3 \ \& \ \leq 5$  and  $>5\times\text{ULN}$ ,
- Total Bilirubin  $> 1.5\times\text{ULN}$  concurrent with  $\text{ALT or AST} > 3\times\text{ULN}$ ,
- Total Bilirubin  $> 2\times\text{ULN}$  concurrent with  $\text{ALT or AST} > 3\times\text{ULN}$

EDISH plots for ALT, AST, and total bilirubin will also be provided.

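### For double-blind laboratory data, the one-visit-per-window rule in SAP 5.6 conflicts with the worst-value and any-time liver-test outputs in SAP 6.8.2, and the SAP does not say which governs

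*SAP*

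**What the plan says.** SAP 5.6 sets the scope: "For PD and clinical laboratory parameters, analysis visits will be derived for the 6m-DB period based on the study day and visit windows". It then gives the selection rule: "If more than one visit falls within a visit window, the visit occurring closest to the target day will be selected". Ties go to the later visit. The paragraph closes with "The derived visits will be used for all analyses", and no exception is written. The text after SAP Table 1 limits the reach in time: "For PD and laboratory parameters assessed during the OLE period and for vital signs and ECG measurements during the entire study, no windowing rules" apply, and the reported visits are used instead.

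SAP 6.8.2 asks for something different. On the ALT, AST, ALP and bilirubin categories, including bilirubin raised together with ALT or AST, it says: "A table will be produced to summarize the number and percentage of patients in each of below category at any post-baseline time point". On shifts it says "Shift tables will be employed to summarize the baseline category versus the" worst category after baseline. It also plans EDISH plots and, optionally, a shift to the maximum CTCAE grade. Protocol 8.2.8 agrees: "Laboratory shift tables from baseline to worst values will be presented".

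Protocol 6.2.3.1 and Table 4 create extra samples after an ALT elevation. A value above 3×ULN is to be confirmed within 2 to 3 days, and no later than 7. Follow-up is two-weekly in the 3–5× band. In the 5–8× band it is weekly at first ("monitoring of LFTs per Table 7 and INR until ALT declines to" 3×ULN), then two-weekly.

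**The concern.** A worst-value table is only as good as the set of values it searches. The extra ALT samples are taken because a patient's ALT is high, so they are the samples most likely to matter for grading. If only one visit per window reaches the analysis, a repeat value higher than the scheduled one never enters the category table, the shift table or the EDISH plot.

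This affects the summaries that carry the placebo comparison. Protocol 8.2.8 makes the double-blind period the basis of the primary safety summaries. Transaminase elevations prompted Protocol Amendment 2 and the introduction of the lower dose. The Amendment 6 rationale places most elevations 3 to 5 months after starting givosiran, which for patients randomized to givosiran falls within the double-blind period. Arms are small: 74/2 = 37 patients each, so one misplaced patient moves a category by 1/37 = 2.7 percentage points.

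**Working it through.** The plan gives no figure to reproduce. The check has three parts.

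**1. How many values survive SAP 5.6.** Window length is last day − first day + 1, from SAP Table 1.

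| Visit | Target | Window | Length (days) |
|---|---|---|---|
| Week 2 | 15 | 2–22 | 21 |
| Month 1 | 29 | 23–43 | 21 |
| Month 2 | 57 | 44–71 | 28 |
| Month 3 | 85 | 72–106 | 35 |
| Month 4 | 113 | 107–127 | 21 |
| Month 5 | 141 | 128–155 | 28 |
| Month 6 | 169 | 156–183 at most | up to 28 |

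Seven windows leave at most seven post-baseline visits per patient. A confirmation sample within 7 days and weekly or two-weekly follow-up will usually share a window with a scheduled visit.

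**2. Worked sampling patterns**, with scheduled visits on their target days:

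- Elevation on Day 85, confirmation on Day 88, weekly to Day 113: 11 values, 7 kept. Days 88, 92, 99 and 106 are dropped; all lie in the Month 3 window at distances 3, 7, 14 and 21 from Day 85, against 0 for the scheduled visit.
- Elevation on Day 85, confirmation on Day 88, two-weekly to Day 141: 10 values, 7 kept. Days 88, 99 and 127 are dropped.
- Weekly from Day 57 to Day 141, confirmation on Day 60: 17 values, 7 kept. All 10 extra values are dropped.

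Under the SAP 6.8.2 wording all 11, 10 and 17 values count. When scheduled visits are off target, a repeat can occasionally be the nearer one, so repeats usually lose rather than always.

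**3. Possible size, under assumed ALT courses.** In multiples of ULN, with peak P on day T:

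- before the peak: ALT(d) = 0.6 + (P − 0.6) × 2^(−(T − d)/u)
- after the peak: ALT(d) = 0.6 + (P − 0.6) × 2^(−(d − T)/h)

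Assumptions: T uniform on Days 60–150; P log-normal with median 5 and log-SD 0.5; scheduled visits within ±7 days (±2 at Week 2); after the first scheduled value above 3, a confirmation 2–7 days later and weekly samples until ALT is at or below 2. There are 8,000 courses per setting and cut.

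Share missed = (patients with a collected value above the cut but no retained value above it) / (patients with a collected value above the cut).

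| u / h (days) | Cut >3×ULN | Cut >5×ULN |
|---|---|---|
| 7 / 14 | 269/4590 = 5.9% | 609/2412 = 25.2% |
| 14 / 14 | 185/5214 = 3.5% | 882/3164 = 27.9% |
| 14 / 28 | 98/5750 = 1.7% | 604/3325 = 18.2% |

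A second set used peaks uniform on 4–12×ULN, a rise of 10–21 days and a decay half-life of 7–21 days (nine settings, 8,000 courses each). It gave 8–26% missed at >5×ULN, and 11–26% of patients above 3×ULN in a lower SAP category. Together the two sets span about 8–28% at >5×ULN.

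The first set samples weekly once ALT exceeds 3×, which is denser than Table 4 requires in the 3–5× band. Neither set uses trial data.

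**The case against.** The strongest reply is that a specific rule should override a general one. SAP 6.8.2 defines its outputs on the worst value or on any time point, and a programmer following it would search every value. SAP 5.6 also has a narrower reading: it may mean only that derived visit labels replace reported ones, since the text after Table 1 contrasts it with data for which reported visits are used. SAP 5.10 puts every assessment before the first open-label dose into the double-blind summaries for patients who enter the extension. SAP 6.8 says that all safety data, whatever the time window, are listed and are summarized for selected laboratory parameters.

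Part of this stands. The outcome is a conflict, and a reader who infers that the peaks definitely vanish goes further than the documents allow. But SAP 5.10 assigns data to study periods, and the windows meant in SAP 6.8 are those of 5.10, so neither settles how many values per visit window are used. The exemption of open-label laboratory data suggests that windowing the double-blind laboratory data was intended.

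It is also true that other outputs keep the events visible: the listing of patients with ALT or AST above 3×ULN or bilirubin above 2×ULN at any time, the full laboratory listing, and the reporting of ALT above 3×ULN as an adverse event of clinical interest. These limit the harm but do not correct a category table or a plot. Finally, safety is descriptive, so no alpha or power is affected.

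**Conclusion.** The conflict between SAP 5.6 and SAP 6.8.2 with Protocol 8.2.8 is plain on the page, and the SAP names no governing rule. It concerns laboratory data in the double-blind period only. Applied as written, SAP 5.6 would under-grade some patients. Under the assumed courses, incidence above 3×ULN is little affected (about 2–6% missed), while roughly 8–28% of patients with a collected value above 5×ULN would have none retained above it. Those shares depend on the assumed peaks, rise and decay times.

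Three stronger readings are tempting and not supported:

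- That the true peaks lie in the repeat samples: the documents give no data on peak timing relative to scheduled visits.
- That the loss falls almost wholly on givosiran: extra samples follow elevations, so it would fall more on the arm with more of them, but no figure by arm is given.
- That losses at 8×ULN measure the damage: the same simulations give 36–47% and 35–57% there, but 8×ULN is a Protocol Table 4 threshold. The SAP's ALT category cuts are 1, 3, 5, 10 and 20×ULN.

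**What to change.** Make two changes to the SAP before the double-blind safety outputs are programmed:

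- In 5.6, replace the closing sentence of the windowing paragraph with one saying that derived visits apply to by-visit summaries and visit-based models only.
- In 6.8.2, add that shift-to-worst, maximum-grade, threshold-category, concurrent ALT/AST and bilirubin, and EDISH outputs use every post-baseline value in the period, whether scheduled, repeat or unscheduled.

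The cost is two sentences and a flag in the laboratory analysis dataset. No new data are needed. The downside is that the liver figures may look slightly less favourable.

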**Table 1: Derived Analysis Visit Windows**

Study Visit	Target Day	Window
Screening	Day -60 to -1	$\leq -1$
Day 1	1	1
Week 2	15	2 – 22
Month 1	29	23 – 43
Month 2	57	44 – 71

Study Visit	Target Day	Window
Month 3	85	72 – 106
Month 4	113	107 – 127
Month 5	141	128 – 155
Month 6	169	156 - the earlier of (Day 183, and the day of the first dose of OLE)

For PD and laboratory parameters assessed during the OLE period and for vital signs and ECG measurements during the entire study, no windowing rules will be implemented, and the reported clinical visits will be used for analysis.

For QOL assessments including SF-12, EQ-5D-5L and missed days of work/school, data are collected every 3 months up to 12 months, then every 6 months afterwards. If the scheduled visits are not performed, any unscheduled and/or discontinuation visits will be mapped to the corresponding scheduled visits if the visit dates fall into below windows. The midpoint of two visits will be included in the time window of the preceding visit.

Scheduled visits (Month 3, 6, 9, 12)  $\pm$  6 weeks

Scheduled visits (Month 18, 24, 30, 36)  $\pm$  12 weeks

For patients who switched from placebo to givosiran, study visits will be mapped based on the redefined baseline.

The derived visits will be used for analyses.

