- ^l For females of child-bearing potential, a serum pregnancy test will be performed at Screening; thereafter, serum or urine pregnancy tests will be performed monthly. Results must be available before dosing.
- ^m At the Month 6 visit, the first open-label dose of givosiran in the extension study will be administered after all scheduled 6-month assessments (for the completion of the double-blind period) have been performed. The urine ALA and PBG sample must be collected prior to the first open-label dose of givosiran. If the ALA and PBG sample collection is delayed due to hemin usage within 4 days of the Month 6 visit, the open-label dose should be delayed as well.
- ⁿ In patients who were on hemin prophylaxis prior to study, collection of the Screening urine samples for ALA, PBG, and ALAS1 mRNA must occur when the patient is not having an attack, and \geq 4 days after prophylactic hemin discontinuation and after their last hemin dose. Two screening urine samples (collected on 2 different days) should be collected for ALA/PBG; one screening urine sample should be collected for ALAS1 mRNA. During the study, spot urine samples for ALA, PBG, and ALAS1 mRNA measurement should be collected prior to study drug dosing; however, if hemin is used for an attack, scheduled urinary ALA, PBG and ALAS1 mRNA will be collected 4 days (+4 days) after the patient's last hemin dose. At the Month 6 visit, the first open-label dose of givosiran should not be administered until the Month 6 urine sample for ALA, PBG have been collected. Where applicable country and local regulations and infrastructure allow, Screening and on-study urine samples for ALA, PBG, and ALAS1 mRNA assessments may be collected by a home healthcare professional, sent to the study center by mail, or brought to the study center at the next visit.

- ^o Where allowed per local regulations and IRB/EC approval, serum, plasma, and urine samples for exploratory biomarker testing, and measuring homocysteine levels, will be collected prior to dosing.
- ^p Genetic testing of porphyria-related genes is only required in patients without prior documented genetic testing for porphyria. See Section 7.6.2 for details.
- ^q Where allowed per local regulations, IRB/IEC approval, and patient consent (and assent, where applicable), a voluntary blood sample may be collected for later DNA analysis. See Section 7.6.2 for details.
- ^r Sample to be collected predose.

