6.3.1. Hemin Prophylaxis

In patients who were on regularly scheduled hemin prophylaxis prior to the study, collection of urine samples for ALA, PBG, and ALAS1 mRNA assessments during Screening must occur ≥ 4 days after prophylactic hemin discontinuation.

Use of hemin for the treatment of acute or ongoing porphyria attacks is allowed during the study and should be recorded as a concomitant medication in the eCRF. If hemin is used for porphyria attacks, scheduled urine samples for ALA, PBG and ALAS1 mRNA assessments will be collected 4 days (with a window of up to 8 days [+4 days]) after the patient's last hemin dose.

Where applicable country and local regulations and infrastructure allow, Screening and on-study urine samples for ALA, PBG, and ALAS1 mRNA assessments may be collected by a home healthcare professional, sent to the study center by mail, or brought to the study center at the next visit.

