## 5.10. Analyses for the Entire Study

The study design includes a 6m-DB period and an OLE period. The primary objective is to evaluate the efficacy and safety of givosiran compared with placebo during the 6m-DB period. In addition, the long-term efficacy and safety of givosiran during the entire givosiran treatment period (beyond 6m-DB) will be characterized for the All Givosiran Treated Set. For patients who received placebo in the 6m-DB period and givosiran in the OLE period, the intra-patient comparison of the two treatment periods will be conducted to assess the trajectory changes for selected efficacy parameters.

The detailed definitions for different treatment periods are as the following.

- **6m-DB Period**

The treatment comparison of givosiran versus placebo will focus on the 6m-DB period, defined as below:

- 1) For patients who received at least one dose of givosiran during the OLE period, all assessments collected prior to the first dose of givosiran in the OLE period will be included in the 6m-DB period. All data will be included in the summary tables and figures.
- 2) For patients who discontinued treatment and did not receive any givosiran dose in the OLE period, all assessments will be included in the 6m-DB period. Assessments collected within given time windows (details listed in below table) will be included in summary tables/figures and those outside the time windows will be listed only unless specified otherwise (e.g., AEs in Section 6.8 ).

Endpoint	Windowing rule for patients who did not enter OLE
Safety and PD endpoints	Assessments with onset date within 28 days of the last dose [1]
Attacks and hemin use related endpoints	Data collected on or before the earlier of 1) Day 162 which is the start day of Month 6 visit window; and 2) end of study (EOS) date.

Endpoint	Windowing rule for patients who did not enter OLE
Other clinical efficacy endpoints	Assessments collected on or before Day 183.

[1] In a rare situation that a patient did not discontinue 6m-DB and did not enter OLE, all data will be included in summary. For AE summary, related AEs will be considered as TEAE and included in summary tables regardless of time window.

- **OLE Period**

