The biomarker endpoints include the ALA levels in AIP patients ( $FAS_{AIP}$ ) at 3 months and 6 months, the urinary PBG levels in AIP patients ( $FAS_{AIP}$ ) at 6 months. Any postbaseline ALA/PBG values measured within 3 days after hemin use during the 6m-DB period will be treated as missing and excluded from analysis. For each biomarker secondary endpoint, the biomarker levels at the specified time point will be estimated and compared between two treatment arms using an MMRM model. The model will include baseline of the corresponding biomarker level as a continuous covariate, stratification factors (prior hemin prophylaxis status and historical attack rates), visit, treatment, and visit by treatment as fixed effects, and patient as a random effect. An unstructured covariance matrix will be used to model the within-subject error. If the fit of the unstructured covariance structure fails to converge, a compound symmetry covariance structure will be used. The least squares (LS) means and the corresponding SEM and 95% CIs for each treatment arm, along with the LS mean difference between two treatment arms at each post-baseline visit will be presented. The p-value for the treatment difference for each endpoint (ALA at Month 3 and Month 6; PBG at Month 6) will be presented. In addition, the overall p values measuring the average treatment effect on ALA and PBG during the entire 6m-DB period will also be reported to assess the durability of the treatment effect. If normal assumptions are violated, a non-parametric Wilcoxon rank sum test will be performed. For ALA at Month 3 and Month 6, if the drop-out rate during the 6m-DB period is  $\geq 5\%$  on the givosiran arm, sensitivity analyses will be performed using a PMM approach as described in Section 9.3.

Daily worst scores for pain measured by BPI-SF in Numeric Rating Scale (NRS), fatigue measured by BFI-SF in NRS, and nausea measured by NRS are collected through eDiary. For each of the symptoms (pain, fatigue and nausea), daily eDiary entries will be averaged into a weekly (i.e. 7 day) score. The change from baseline in weekly mean scores is defined as the post-baseline weekly mean score minus the baseline score. The AUC of change from baseline over 6 months in the respective measure will be calculated for each patient based on change from

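### SAP Table 1 closes the Month 6 biomarker window at Day 183, so a valid hemin-delayed ALA/PBG sample taken later, but before the first OLE dose, is dropped; the expected loss is small

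*SAP*

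**What the plan says.** **Collection (protocol).** Table 1 places the Month 6 visit at Day 169 ±7, that is Day 162 to 176. After hemin for an attack, footnote n requires that "scheduled urinary ALA, PBG and ALAS1 mRNA will be collected 4 days (+4 days) after the patient's last hemin dose"; Section 6.3.1 repeats the 4 to 8 day interval. Footnote m ties the first open-label dose to the urine specimen: "collection is delayed due to hemin usage within 4 days of the Month 6 visit, the open-label dose should be delayed as well". No latest day is stated for either.

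**Validity (SAP 6.5.2).** "Any postbaseline ALA/PBG values measured within 3 days after hemin use during the 6m-DB period will be treated as missing and excluded from analysis". A sample taken four or more days after hemin is therefore usable.

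**Study period (SAP 5.10).** For patients who receive an OLE dose, "all assessments collected prior to the first dose of givosiran in the OLE period will be included in the 6m-DB period". There is no day limit.

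**Analysis visit (SAP 5.6 and Table 1).** The Month 6 window is Day "156 - the earlier of (Day 183, and the day of the first dose of OLE", and "The derived visits will be used for all analyses". PD samples in the OLE period are not windowed, but under Section 5.10 that period begins only with the first OLE dose, so this exemption does not reach a sample taken before it.

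**The concern.** The protocol holds the first open-label dose so that a clean double-blind Month 6 sample can be obtained. For OLE entrants the limit at the first OLE dose already keeps open-label samples out of Month 6. The additional Day 183 cap can then remove a sample that the protocol deliberately waited for.

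ALA and PBG at Month 6 are the second and third secondary endpoints in the fixed testing sequence (SAP 3.2.2 and 5.7). Whether a sample is lost depends on hemin use around Month 6, which is related to outcome. The planned sensitivity analysis would not respond: the pattern mixture model for ALA is triggered by the drop-out rate (SAP 6.5.2 and 9.3), these patients have not dropped out, and PBG has no such model.

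**Working it through.** **1. Reproducing the window.** Limits at midpoints between target days give (141 + 169)/2 = 155, so Month 6 opens on Day 156, and (169 + 197)/2 = 183, so it closes on Day 183. Both match Table 1. The same rule gives the other upper limits (22, 43, 71, 127, 155) except Month 3, where it gives (85 + 113)/2 = 99 and the table has 106. Month 3 thus extends 106 − 85 = 21 days past target and Month 6 only 183 − 169 = 14, with no reason stated.

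**2. Day arithmetic.** With last hemin dose on Day H, the sample is due on Day H + 4 to H + 8.

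| Last hemin dose | Sample due | Mapped to Month 6? |
|---|---|---|
| Day 175 or earlier | Day 183 or earlier | always |
| Day 176 | Day 180–184 | lost only at the full 8 days |
| Day 177–178 | Day 181–186 | depends on the delay |
| Day 179 | Day 183–187 | kept only at 4 days |
| Day 180 or later | Day 184 or later | never |

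If the visit is in window and hemin has ended by the visit day, one combination misses the window: last dose on Day 176 with an 8-day delay, giving Day 184. Every step of that path follows the protocol.

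**3. How often.** Inputs from SAP 5.1: 8 attacks per year on placebo and 4.4 on givosiran, with dispersion from the 6-month figures: (2.9² − 4)/4² = 0.276 and (1.8² − 2.2)/2.2² = 0.215. A 2 to 5 day hemin course is taken from Protocol 1.1. Assumptions: every attack is treated with hemin; re-collection is uniform over 4 to 8 days and is put off again if a new course intervenes. The 7 to 14 day course is also an assumption; Protocol 1.1 says only that some attacks last several weeks with prolonged hemin. Gamma-Poisson simulation, 40,000 patients per arm and scenario:

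| Course | Visit day | Placebo delayed | Placebo after Day 183 (of 35) | Givosiran after Day 183 (of 35) |
|---|---|---|---|---|
| 2–5 days | 169 | 13.1% | 0.72% (0.25) | 0.22% (0.08) |
| 2–5 days | uniform 162–176 | 12.9% | 1.21% (0.43) | 0.52% (0.18) |
| 2–5 days | 176 | 13.0% | 4.80% (1.68) | 2.44% (0.85) |
| 7–14 days | 169 | 24.8% | 7.95% (2.78) | 3.65% (1.28) |
| 7–14 days | uniform 162–176 | 25.1% | 9.28% (3.25) | 4.24% (1.48) |

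In the second row, 1 − 1.21/12.9 = 91% of delayed placebo samples are kept. With fixed 4-day and 8-day delays included, the placebo range is 0.04 to 2.9 of 35 for short courses and 1.7 to 7.2 for long ones. The upper ends need every patient to attend on Day 176 and every sample to take the full 8 days. A different long-course assumption (one day plus an exponential with mean 7) gives 21% delayed and 6% late, about 2 of 35.

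**4. Effect on precision.** SAP 9.1.2 plans ALA means (SD) of 20.0 (11.1) and 2.3 (1.1) at Month 3; assume the same at Month 6. Unadjusted z with 35 per arm is 17.7/√(11.1²/35 + 1.1²/35) = 9.4. With three placebo values lost it is 17.7/√(11.1²/32 + 1.1²/35) = 9.0.

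**The case against.** The strongest reply has four parts.

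- **Rarity.** With the protocol's own course length, less than one patient is expected to be affected. The simulation also leans high, because attacks may be treated without hemin (Protocol 3.5 and 6.3). This stands. A reader might infer that hemin-delayed Month 6 samples are discarded in general; the window runs 7 days past the latest in-window visit, and most are kept.
- **Different purposes.** The protocol governs collection, SAP 5.10 assigns data to a period, and Table 1 assigns samples to visits. Day 183 is a midpoint, not an arbitrary choice. This is fair, but it does not give the late sample a visit.
- **Consequence.** The MMRM keeps the patient's earlier visits, and losing high placebo values would tend to shrink the treatment difference. Both points are reasonable, although the documents give no data on the lost values, and the rank-test fallback in SAP 6.5.2 states no handling of missing values.
- **A cap is defensible.** Day 183 is already 42 days after the scheduled Month 5 dose (Day 141). SAP 9.3 assumes the effect is maintained for up to 56 days, to about Day 197. A missed open-label dose (Protocol 6.2.2 allows for missed doses) could let an unlimited window take in Month 6.5 or Month 7 samples. This stands, and it means that simply removing the cap is not the right repair.

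**Conclusion.** The mismatch is real and can be read directly from the text: a valid, protocol-compliant, pre-OLE Month 6 sample on Day 184 or later is double-blind data without an analysis visit, and it drops out of the Month 6 ALA and PBG comparisons. It is a minor point. In the central short-course scenario the expected loss is well under one of 35 placebo patients; in the assumed long-course scenarios it is about 2 to 3. Givosiran loses about half as many or fewer.

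These sizes rest on the design attack rates, on every attack receiving hemin, and on the assumed course lengths and visit timing. A reader might also infer that the lost samples are known to be mostly placebo. The documents do not say so. It is an inference from the planned rates, under which 8/(8 + 4.4) = 65% of attacks are on placebo. The likely effect on the estimate is small, and nothing here threatens the trial's conclusions. The change is worth making because it is nearly free and removes hemin-related missingness that the planned sensitivity analysis would not detect.

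**What to change.** Amend the Month 6 row of SAP Table 1.

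- **Patients who enter the OLE:** map to Month 6 the protocol-delayed Month 6 sample taken on or before the first OLE dose (pre-dose), even if it falls after Day 183. Keep the closest-to-target rule, and do not map samples collected for Month 6.5 or Month 7.
- **Patients who never receive an OLE dose:** keep Day 183 and reconcile it with SAP 5.10, which limits summarized PD data to 28 days after the last dose for patients who discontinued. A last dose on Day 141 gives 141 + 28 = Day 169, so the two rules differ.
- **Sensitivity analysis:** repeat the Month 6 ALA and PBG comparisons with the Day 183 cap, because the mapped late values lie further from the last double-blind dose.

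The cost is one table cell, a sentence of text and one rerun. It needs no new data and changes no clinical rule. If the analysis has already been done, count the unmapped pre-OLE samples by arm and rerun with them included.
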